1.0 Background

Chemotherapy-induced peripheral neuropathy (CIPN) is a dose and age-dependent side-effect associated with six main antitumor agent drug classes: platinum-based drugs, (e.g., oxaliplatin), taxanes (e.g., paclitaxel and docetaxel), vinca alkaloids (e.g., vincristine), epothilones (e.g., ixabepilone), the proteasome inhibitors (e.g., bortezomide) and immunomodulatory drugs (e.g., thalidomide)[1]. In a review of over 30 clinical studies, CIPN prevalence was reported to be approximately 68% when measured in the first month after finishing a variety of chemotherapy agents, most of which had been associated with CIPN; it was 60% at three months and 30% at 6 months or more [2].

CIPN remains a challenge to treat, as most agents used in practice, such as tricyclic antidepressants, anticonvulsants (gabapentin and pregabalin), or serotonin-norepinephrine reuptake inhibitors (SNRIs), primarily duloxetine, provide limited benefit to most patients and can have significant side effects[3-5].

The mechanism of CIPN broadly includes the production of neuronal toxicity and inflammation[6]. The six main classes of antitumor agents, discussed above, cause damage to peripheral sensory, motor, and autonomic neurons, through such mechanisms as microtubule disruption, oxidative stress and mitochondrial damage, altered ion channel activity, and myelin sheath and DNA damage [7]. In addition, the cumulative damage leading to increased activation of the immune system ultimately promotes cell damage and death in peripheral neurons, leading to a sensitization to nociceptive responses[6].

The cannabinoids, delta-nine-tetrahydrocannabinol (THC) and cannabidiol (CBD), derived from the plant *Cannabis sativa* (*Cannabis*) have shown some efficacy in the treatment of pain [8, 9], including neuropathic pain[3, 10]. THC interacts with the endocannabinoid system primarily through the activation of cannabinoid 1 (CB₁) and cannabinoid 2 (CB₂) receptors[11]. CBD does not efficiently interact to activate known cannabinoid (CB₁ and CB₂) receptors [12]. CBD, however, can antagonize the activity of CB₁ and CB₂ receptor agonists [13].

THC and additional CB₁ and CB₂ receptor agonists, have been shown to be effective at reducing CIPN in multiple preclinical models [6, 14]. THC and additional cannabinoids, through CB1 and/or CB2 receptors, have the potential to modulate pain through a variety of mechanisms, including inhibition of calcium channel activity, transient receptor potential (TRP) channels, serotonin, GABA and glutamate receptor signaling, and modulation of the immune system, leading to anti-inflammatory activity [15-17]. Inhaled cannabis has also been reported to be effective for treating HIV-associated neuropathy, possibly via CB₁ agonism [18].

Neuropathic pain may also involve abnormal hyper-excitability in skin afferent nerves. Skin cells express CB2 and endothelin receptors, and when activated, they release B-endorphin, which can reduce hyperalgesia, that is mediated by pro-inflammatory pathways [19, 20].

CBD has been shown to have pleotropic effects that ultimately lead to reduction in oxidative stress and inflammation [21]. Increasingly, preclinical evidence demonstrates that CBD has anti-neuropathic pain effects in multiple rodent models, including models of CIPN [21-25]. Also, there is significant overlap with mechanisms controlling pain when CBD and THC are compared. CBD has been shown to inhibit pain through modulation of calcium and TRP channels, serotonin receptors, glycine receptors, and modulation of the immune system [6], in particular, microglia and macrophage function [26], leading to anti-inflammatory activity.

Similar to CB₁ and CB₂ receptor agonists, the neuroprotective and anti-inflammatory properties of CBD provide a potential mechanism for the protective effects of CBD in neuropathic pain, including CIPN [27]. For example, CBD has been shown to directly or indirectly modulate several receptors involved in modulating pain signaling, including 5-HT_{1A} [25], and transient receptors TRPV1 and TRPA1

2.0 Goals

This is a pilot randomized double blinded placebo controlled cross-over trial. This pilot study will randomize 40 patients with chemotherapy-induced peripheral neuropathy to receive, for 14 days, either 1) a CBD cream or 2) a placebo. Patients initially receiving the placebo will cross over to receive the CBD cream, while those receiving the CBD creams will cross over to receive the placebo, for 14 days. Patients will apply cream to the affected area (hands and/or feet) twice daily (morning and evening). This cross-over will allow all patients to eventually receive the CBD cream and will allow us to determine whether any benefit derived from a CBD preparation will diminish or persist after the CBD preparation is stopped (that is in the patients who initially received the CBD product and then were changed to receive a placebo, while still being blinded to what they received).

No washout period is planned with the cross-over because a) no washout is needed in patients going from placebo to CBD cream, and b) we want to determine what happens after patients stop cannabis cream, i.e., do the effects persist after the patient starts the placebo portion, as was prominently seen in a prior trial of ours evaluating capsaicin cream [30].

2.1 Primary Objective

The aims of the proposed project include:

1. To evaluate whether topical CBD improves chemotherapy-induced peripheral neuropathy (CIPN), compared to placebo
2. To evaluate side effects from topical CBD cream use, compared to placebo

The data obtained from this trial are designed to provide information to allow for a larger phase III, placebo-controlled, randomized, clinical trial.

Primary endpoint

The primary endpoint is change in CIPN from baseline to the end of week 2. CIPN will be measured by the sensory subscale of the EORTC QLQ-CIPN20 which is composed of 9 individual items.

2.2 Secondary Goals

Secondary endpoints include other measures of neuropathy as measured by the EORTC QLQ CIPN20 motor subscale, the EORTC QLQ CIPN20 autonomic scale, and the total CTCAE neuropathy scale. Adverse event profiles will also be assessed using symptom questionnaires and CTCAE v5.0.

3.0 Registration Patient Eligibility

3.1 Registration - Inclusion Criteria

- 3.11 Age \geq 18 years
- 3.12 English speaking
- 3.13 Cancer diagnosis of any tumor type with chemotherapy-induced neuropathy
- 3.14 At least 4 out of 10 severity of neuropathy pain and/or tingling per appendix IV
- 3.15 Stable for at least 7 days prior to registration on medications for neuropathy, if any are being used
- 3.16 ECOG Performance Status (PS) 0, 1 or 2 (Appendix VIII).
- 3.17 **Negative pregnancy test done \leq 7 days prior to registration, for persons of childbearing potential only.**

NOTE: If a urine test is positive or cannot be confirmed as negative, a serum pregnancy test will be required.

- 3.18 Able to provide written informed consent
- 3.19a Ability to complete questionnaire(s) by themselves or with assistance.
- 3.19b No evidence of residual cancer
- 3.19c Required Initial Laboratory Values: Following completion of chemotherapy, patients must have had a CBC and serum chemistries, including the following:
 - Platelet count $>$ 100,000/mm³
 - Absolute neutrophil count (ANC) \geq 1,000/mm³
 - Hemoglobin $>$ 11 g/dL
 - Serum transaminase [ALT or AST] \leq 1.2 x upper limit of normal (ULN)
 - Alkaline phosphatase \leq 1.2 x ULN
 - Serum creatinine \leq 1.2 x ULN

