3.2 Registration - Exclusion Criteria

- 3.21 Any of the following because this study involves an investigational agent whose genotoxic, mutagenic and teratogenic effects on the developing fetus and newborn are unknown:
 - Pregnant persons
 - Nursing persons
 - Persons of childbearing potential who are unwilling to employ adequate contraception
- 3.22 Any medical condition that would prohibit use of a topical cream (skin infection or open wound in the area of the neuropathy)
- 3.23 Co-morbid systemic illnesses or other severe concurrent disease which, in the judgment of the investigator, would make the patient inappropriate for entry into this study or interfere significantly with the proper assessment of safety and toxicity of the prescribed regimens.

- 3.24 Pre-existing neuropathy prior to chemotherapy that would confuse the issue of CIPN
- 3.25 Currently on chemotherapy or received chemotherapy treatment within the prior 3 months.
- 3.26 Use of other cannabis products within 30 days prior to registration
- 3.27 History of allergy to cannabis products

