4.0 Test Schedule

4.1 Test schedule for Chemotherapy-Induced Peripheral Neuropathy

Study Visit	1	2	3	4	5	6	7
Study Time Point	Screening /Baseline (Day -30 to Day 1)	Day 1	End of Week 1	End of Week 2 ^c (+3 Days)	End of Week 3	End of Week 4	End of study
CLINICAL ASSESSMENTS							
Informed consent	X						
Inclusion/exclusion criteria	X ^g						
Demographics/ Medical history	X						
Pregnancy testing ^a	X						
Randomization	X						
Dispense Study Product/Placebo		X		X			
Collect questionnaires							X
Adverse event assessment ^b			X	X	X	X	
STUDY TESTING							
EORTC QLQ-CIPN 20 instrument (Appendix I)	X		X	X	X	X	
Global impression of change (Appendix II)			X	X	X	X	
Chemotherapy Induced Peripheral Neuropathy Assessment Tool (Appendix III)	X		X	X	X	X	
Symptom experience diary (Appendix Va & Vb)	X ^d		X ^e	X ^e	X ^e	X ^e	
NCI-CTCAE neuropathy scale ^f (Appendix VI)	X		X	X	X	X	
Cycle = 14 days							
^a For individuals of childbearing potential. Must be done \leq 7 days prior to registration.							
^b Research nurse or clinician to call patient. Including inquiry about skin toxicity and to assess for suicidal thoughts (Appendix IX). Ask the patient if they have missed any doses of the study							

medication and provide education if necessary. Note any other pertinent information that the patient provides.

^c After subject completes week 2 they will turn in completed questionnaire diary and start the next supply of cream within 1-3 days after completing the first 2 weeks, ideally.

^d Appendix Va: System Experience Diary used for baseline assessment. Must be completed prior to application of study medication.

^e Appendix Vb: System Experience Diary used for weekly assessments. Must be completed at the end of each week.

^f To be completed during research nurse or clinician call to patient per Appendix VI.

^g Required Initial Laboratory Values per inclusion criteria 3.19c can be done any time after the patient has completed their chemotherapy and prior to study registration.

5.0 Stratification Factors:

- Gender (Male, Female, or Other)

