15.1 CBD Cream**15.11 Drug procurement:**

Nightingale Remedies will supply all drug. Each institution will order the drug from Nightingale Remedies. Submit the Drug Order Form request to:

Outdated or remaining drug is to be destroyed on-site per procedures in place at each institution.

The investigator is responsible to ensure supervision of accurate monitoring of the receipt, storage and allocation of the study product. Copies of all invoices of shipments must be retained. Accurate study product inventory, dispensing and accountability logs must be obtained and stored in the Pharmacy Binder.

15.111 Each participating institution may ship Study Product/Placebo directly to their patients if the site standards allow. All local site procedures should be followed and accurate accountability logs should be maintained.

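### The pregnancy test is timed to registration, and nothing visible limits the time from registration to first application, so a test about 30 days old at first exposure complies with the protocol

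*Combined protocol and SAP*

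**What the plan says.** Section 3.17 makes a negative pregnancy test an inclusion criterion, to be done no more than "7 days prior to registration, for persons of childbearing potential only". Footnote a to the test schedule in section 4.1 ("For individuals of childbearing potential. Must be done") repeats the 7-day limit and again counts back from registration.

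In that schedule, consent, eligibility, pregnancy testing and randomization are all marked under Visit 1, headed "Screening /Baseline (Day -30 to Day 1)". Visit 2 is Day 1, and the only entry in its column is "Dispense Study Product/Placebo". Pregnancy testing is marked once and not repeated.

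Section 6.11 requires registration to be complete before treatment starts, and section 6.2 has eligibility verified before a registration is accepted. Neither sets a longest interval from registration to first application.

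Section 3.21 gives the reason for excluding pregnant and nursing persons: the agent's "genotoxic, mutagenic and teratogenic effects on the developing fetus and newborn are unknown". The same criterion excludes persons of childbearing potential who will not use adequate contraception.

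Section 3.22, also a registration criterion, excludes conditions that rule out a topical cream and names "skin infection or open wound in the area of the neuropathy". It has no time point of its own. The baseline diary (Appendix Va) asks about rash on hands or feet and, under footnote d, must be filled in before any cream is applied.

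**The concern.** The reason given in 3.21 concerns exposure of a fetus to the cream, and exposure begins at first application. The 7-day limit counts back from registration, which the schedule lets fall up to a month earlier. A site can follow 3.17, footnote a and the Visit 1 window exactly and still start treatment on a test that no longer describes the patient's current status. What is at stake is a participant-safety safeguard. Sample size, power and the primary analysis are not affected.

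The skin criterion has the same structure. A wound or infection that appears after registration but before Day 1 would meet no scheduled check against 3.22 before cream is applied.

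**Working it through.** The plan states no figure for the interval from test to first application, so there is none to reproduce. The check is calendar arithmetic on the stated windows.

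**Inputs**
- Test to registration: at most 7 days (3.17; 4.1 footnote a).
- Visit 1, holding test, eligibility and randomization: Day -30 to Day 1 (4.1).
- First dispensing: Day 1 (4.1). First application is assumed to be on Day 1.
- Registration to Day 1: no limit in the visible text (3, 4.1, 6).

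**Longest permitted test age at first application**

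Test age = (test to registration) + (registration to Day 1).

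| Reading | No Day 0 | With Day 0 |
|---|---|---|
| Day -30 to Day 1 | 30 days | 31 days |
| Test on Day -30, registration 7 days later: registration to Day 1 | 30 - 7 = 23 days | 31 - 7 = 24 days |
| Test age in that case | 7 + 23 = 30 days | 7 + 24 = 31 days |
| Window read as limiting registration only, test 7 days before a Day -30 registration | 30 + 7 = 37 days | 31 + 7 = 38 days |

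The schedule marks the test inside Visit 1, so 30 to 31 days is the natural reading, and 37 to 38 days needs a looser one. Relative to the 7-day limit, 30 / 7 is about 4.3. At the other extreme, testing, registration and dispensing on one day also complies, giving a test age of 0 days.

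**Effect of each remedy**
- Same 7-day limit counted back from first application: longest test age 7 days.
- Registration to Day 1 capped at k days: longest test age 7 + k days. For illustration only, k = 7 gives 7 + 7 = 14 days, so the two remedies are not interchangeable. The documents supply no k.

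**Skin criterion**

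Registration may fall on Day -30, so the judgement under 3.22 can be 30 days old (31 with a Day 0) at first application. The one scheduled record required before application is the baseline diary. In the text shown it asks about rash only, it is self-reported, it sits in the same Visit 1 window, and no action is attached to the answer. It does not re-check for infection or an open wound.

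**The case against.** **Permitted, not planned.** Thirty days is the extreme of a window that equally allows same-day registration and dispensing, and nothing suggests long gaps are expected. Registration is also the protocol's common anchor (3.15, 3.26), so 3.17 is consistent in form. This stands. The point concerns what the wording allows, and a 7-day limit at first application is not something the protocol states.

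**Contraception.** Section 3.21 also requires adequate contraception, and treatment runs about four weeks (2 x 14 = 28 days) with no repeat test. Even a test on Day 1 would be about 28 days old by the last application. The protocol therefore already relies on contraception during exposure, and pregnancies are reported and followed under 10.55. This limits the gain from a change. It does not remove the mismatch, because the protocol asks for a timed test in addition to contraception.

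**Unseen material.** The schema figure is not shown and the Eligibility Checklist Form is not among the documents. Either could carry a limit, so the finding holds for the visible text only.

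**Stronger readings the documents do not support**
- A reader might infer that the side-effect comparison with placebo is biased. Assignment is randomized and double-blind, so lesions arising before Day 1 should not favour either arm systematically. At most they add noise.
- A reader might infer that skin is first asked about at the end of week 1. That is the first scheduled staff call, but the baseline diary asks about rash before application.
- A reader might infer that patients are not seen on Day 1. Shipping is optional ("Each participating institution may ship Study Product/Placebo directly to their patients if the site standards allow"). Section 6.4a describes staff dispensing at the site.
- A reader might think Appendix IX questions 2 and 3 could serve as a Day 1 eligibility check. They ask about irritation, rash, blisters and open areas where cream is applied. They do not mention pregnancy, nursing, contraception or infection, so they cannot confirm 3.21.

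**Conclusion.** The point holds as a gap between the wording of 3.17 with footnote a and the Visit 1 window in 4.1. Following the rules exactly permits a pregnancy test about 30 days old at first application, 31 if a Day 0 is counted, against a 7-day limit that runs only to registration. This fits poorly with the reason given in 3.21.

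The conclusion rests on three assumptions: Day 1 is the day of first application, the test is done within the Visit 1 window, and no limit exists in material not provided. Shipping could lengthen the interval if application follows dispensing by some days. How often long intervals would occur cannot be judged from the documents, and the contraception requirement makes the residual risk smaller than the interval alone suggests.

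The skin criterion is a secondary point of the same kind. The change is worth making because it bears on a safety safeguard and needs few words. It does not call the efficacy or side-effect comparisons into question.

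**What to change.** Reconcile 3.17 and footnote a with the Visit 1 window in 4.1. Either route closes the gap, and the choice and the interval belong to the sponsor:

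1. Count the limit on the existing test back from first application of cream instead of from registration. Keep the test before registration, so that a positive result cannot appear in a patient already randomized.
2. Keep the registration anchor and state in 4.1 or section 6 a maximum of k days from registration to Day 1. Test age is then bounded at 7 + k days.

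Under either route, state that Day 1 means the day of first application, so that the limit also covers shipped product.

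Route 2 also limits the age of the judgement under 3.22, to k days if that judgement is made on the day of registration. Route 1 applied to the pregnancy test alone leaves 3.22 as it is for patients who need no test.

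The cost is scheduling: testing and registration must sit closer to dispensing, with time for relabelling by the pharmacist and any shipping fitted inside the interval. Neither route adds a test or an instrument, and neither changes the sample size or the analysis.

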3.2 Registration - Exclusion Criteria

- 3.21 Any of the following because this study involves an investigational agent whose genotoxic, mutagenic and teratogenic effects on the developing fetus and newborn are unknown:
 - Pregnant persons
 - Nursing persons
 - Persons of childbearing potential who are unwilling to employ adequate contraception
- 3.22 Any medical condition that would prohibit use of a topical cream (skin infection or open wound in the area of the neuropathy)
- 3.23 Co-morbid systemic illnesses or other severe concurrent disease which, in the judgment of the investigator, would make the patient inappropriate for entry into this study or interfere significantly with the proper assessment of safety and toxicity of the prescribed regimens.

- 3.24 Pre-existing neuropathy prior to chemotherapy that would confuse the issue of CIPN
- 3.25 Currently on chemotherapy or received chemotherapy treatment within the prior 3 months.
- 3.26 Use of other cannabis products within 30 days prior to registration
- 3.27 History of allergy to cannabis products

4.0 Test Schedule

4.1 Test schedule for Chemotherapy-Induced Peripheral Neuropathy

Study Visit	1	2	3	4	5	6	7
Study Time Point	Screening /Baseline (Day -30 to Day 1)	Day 1	End of Week 1	End of Week 2 ^c (+3 Days)	End of Week 3	End of Week 4	End of study
CLINICAL ASSESSMENTS							
Informed consent	X						
Inclusion/exclusion criteria	X ^g						
Demographics/ Medical history	X						
Pregnancy testing ^a	X						
Randomization	X						
Dispense Study Product/Placebo		X		X			
Collect questionnaires							X
Adverse event assessment ^b			X	X	X	X	
STUDY TESTING							
EORTC QLQ-CIPN 20 instrument (Appendix I)	X		X	X	X	X	
Global impression of change (Appendix II)			X	X	X	X	
Chemotherapy Induced Peripheral Neuropathy Assessment Tool (Appendix III)	X		X	X	X	X	
Symptom experience diary (Appendix Va & Vb)	X ^d		X ^e	X ^e	X ^e	X ^e	
NCI-CTCAE neuropathy scale ^f (Appendix VI)	X		X	X	X	X	
Cycle = 14 days							
^a For individuals of childbearing potential. Must be done \leq 7 days prior to registration.							
^b Research nurse or clinician to call patient. Including inquiry about skin toxicity and to assess for suicidal thoughts (Appendix IX). Ask the patient if they have missed any doses of the study							

medication and provide education if necessary. Note any other pertinent information that the patient provides.

^c After subject completes week 2 they will turn in completed questionnaire diary and start the next supply of cream within 1-3 days after completing the first 2 weeks, ideally.

^d Appendix Va: System Experience Diary used for baseline assessment. Must be completed prior to application of study medication.

^e Appendix Vb: System Experience Diary used for weekly assessments. Must be completed at the end of each week.

^f To be completed during research nurse or clinician call to patient per Appendix VI.

^g Required Initial Laboratory Values per inclusion criteria 3.19c can be done any time after the patient has completed their chemotherapy and prior to study registration.

5.0 Stratification Factors:

- Gender (Male, Female, or Other)

6.0 Registration/Randomization Procedures

6.1 Registration (Step 1):

6.11 Registering a patient

To register a patient, access the Registration Application at [REDACTED] The Registration Application is available 24 hours a day, 7 days a week. If unable to access the application, contact the Mayo Clinic Research Registration Office

[REDACTED] between the hours of 8am and 4:30 pm Central Time, Monday through Friday. Prior to initiation of protocol treatment, this process must be completed in its entirety and a MCCC Subject ID number (R#####) must be assigned. It is the responsibility of the individual registering the patient to confirm the process has been successfully completed prior to release of the study agent.

